	
16. Any uncontrolled, intercurrent illness including but not limited to ongoing or active infection, symptomatic congestive heart failure, unstable angina pectoris, symptomatic cardiac arrhythmia.
 
17. Has a known additional malignancy that is progressing or requires active treatment. [Exception also include: Basal cell carcinoma of the skin or squamous cell carcinoma of the skin that has undergone potentially curative therapy, or in situ cervical cancer.]
 
18. Any other serious medical or psychiatric illness/condition likely in the judgment of the Investigator(s) to interfere or limit compliance with study requirements/treatment
 
19. Treatment for active HCV within 60 days of study entry. [Note: Untreated HCV positive subjects are eligible, and if stable on pembrolizumab for 6 months after study entry, consideration may be given to starting anti-HCV therapy, at the discretion of the treating Investigator.]
 
20. HCC patients with evidence of prior HBV must fulfill the following criteria in order to be eligible for the study: HBV VL <100 IU/mL before study enrollment, and subjects with active HBV need to be on anti-HBV suppression ≥ 3 months, throughout treatment and for at least 6 months after completion of therapy.

--	---

PROTOCOL SCHEMA

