14	Known active central nervous system (CNS) metastases and/or carcinomatous meningitis. [Exception: Subjects with previously treated brain metastases may participate provided they are stable (without evidence of progression by imaging, for at least 4 weeks prior to the first dose of study drug and any neurologic symptoms have returned to baseline), have no evidence of new or enlarging brain metastases, and are not using steroids for at least 7 days prior to trial treatment. This exception does not apply to carcinomatous meningitis which is excluded regardless of clinical stability.]

15	Is pregnant or breastfeeding, or expecting to conceive or father children within the projected duration of the trial through 120 days after the last dose of trial treatment.
16	Any uncontrolled, intercurrent illness including but not limited to ongoing or active infection, symptomatic congestive heart failure, unstable angina pectoris, cardiac arrhythmia.
17	Has a known additional malignancy that is progressing or requires active treatment. [Exception: Basal cell carcinoma of the skin or squamous cell carcinoma of the skin that has undergone potentially curative therapy, or in situ cervical cancer.]
18	Any other serious medical or psychiatric illness/condition likely in the judgment of the Investigator(s) to interfere or limit compliance with study requirements/treatment.
19	Treatment for active HCV within 60 days of study entry. [Note: Untreated HCV positive subjects are eligible, and if stable on pembrolizumab for 6 months after study entry, consideration may be given to starting anti-HCV therapy, at the discretion of the treating Investigator.]
20	HCC patients with evidence of prior HBV must fulfill the following criteria in order to be eligible for the study: HBV VL <100 IU/mL before study enrollment, and subjects with active HBV need to be on anti-HBV suppression ≥ 3 months, throughout treatment and for 6 months after.

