6.0 Enrollment Procedures

To enter a patient, the Investigator or Study Team will contact the Clinical Research Services' (CRS) Representative. All eligibility requirements must be reviewed prior to the patient entering the study. The following information must be provided to the CRS Representative:

- 1) Completed and signed protocol-specific eligibility checklist;
- 2) All pages of the original signed informed consent form (ICF) including HIPAA Form B;
- 3) Relevant source documents including but not limited to: subject medical history and physical exam, concomitant medications, admission or discharge notes, diagnostic reports, pathologic confirmation of diagnosis, and relevant subject-specific written communication.

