Evaluation of subjects with elevated transaminases, bilirubins, and alkaline phosphatase should involve a workup to assess for infection (SBP or other), viral reactivation (if relevant), vascular thrombosis, biliary obstruction, possible hepatotoxic medications, tumor progression, alcohol toxicity, and effects of pembrolizumab. At baseline, all subjects should be assessed for HBsAg, HBsAb, anti-HBc antibody, HBeAg, and anti-HCV. As described above, a viral load <100 IU/mL is required for study entry, and with active HBV must have also been treated with antiviral therapy for ≥ 3 months before initiation of study treatment. Subjects with controlled HBV on therapy should stay on this same therapy throughout pembrolizumab treatment. Subjects who are positive for HBsAg or anti-HBc (but negative for HBsAg and HBV DNA), should be assessed for HBV viral load, HBsAg, HBsAb, anti-HBc antibody, HBeAg every 3 weeks, independent of treatment delays.

Subjects with chronic infection by hepatitis C virus (HCV) with successful treatment (defined as SVR12 or SVR24) may be included. HCV genotype should also be recorded at baseline. **Untreated HCV positive subjects are eligible, and if stable after 6 months on pembrolizumab, additional antiviral treatment for HCV may be considered per local standard of care.** Viral loads should be assessed for those with an underlying viral etiology q 3 weeks. They should also be checked if there is an elevation in ALT $> 3 \times$ baseline, a tenfold or greater increase in HBV or HCV DNA $>$ baseline, or an absolute increase in HBV or HCV DNA $> 10^5$ c/mL. If evidence of reactivation is present, the Sponsor should be consulted within 24 hours, and pembrolizumab treatment should be interrupted. A hepatology consult should be obtained.

- For **Grade 2** AST/ALT or alkaline phosphatase events (if normal or Grade 1 at baseline) and no other etiology is found, monitor liver function tests weekly.

- For **Grade 3-4** AST/ALT, alkaline phosphatase events if normal at baseline), or $>3\times$ baseline (if greater than $2\times$ ULN at baseline) and no other underlying etiology is found, consider treatment with intravenous corticosteroids for 24–48 hours. When improved to baseline (for those with levels $\geq 2\times$ ULN at baseline) or Grade 1 or less (for those with normal baseline values), a steroid taper should be started and continued over no less than 4 weeks.

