10.2.1 Hepatic Toxicity

At baseline, all subjects should be assessed for HBsAg, HBsAb, anti-HBc antibody, HBeAg, and anti-HCV. Patients who test negative for these hepatitis labs do not need to repeat these lab tests again, unless clinically indicated. Evidence of prior HBV should also prompt a viral load measurement at baseline. A viral load <100 IU/mL is required for study entry. Those with active HBV must have been treated with antiviral therapy for ≥3 months before initiation of study treatment. Subjects with controlled HBV on therapy should stay on this therapy throughout pembrolizumab. Subjects who are positive for HBsAg, or anti-HBc (but negative for HBsAg and HBV DNA), should be assessed for viral loads, anti-HBs, anti-HBc and HBsAg every 3 weeks (Q3W), independent of treatment delays.

Viral loads and HBsAg should also be assessed if there is an elevation in ALT >3× baseline, a tenfold or greater increase in HBV or HCV DNA over baseline, or an absolute increase in HBV or HCV DNA over 10⁵ c/mL. **If evidence of reactivation is present, the Sponsor should be consulted within 24 hours, and pembrolizumab treatment should be interrupted.**

If there is a 5X or greater elevation in ALT (if normal at baseline), workup should be undertaken to rule out SBP, obstruction, medication, or vascular injury. If these are unrevealing, consideration of pembrolizumab toxicity should be undertaken. Steroids may be considered if viral flare and other etiologies are ruled out.

Table 1: Hepatitis Treatment Guidelines

Test(s)	Patient Status	Included in KN-0224	Any HBV Treatment Needed?
HBsAg (-) Total anti-HBc (+) Anti-HBs (+)	Immune after natural infection	YES	NO
HBsAg (-) Total anti-HBc (-) Anti-HBs (+)	Immune after vaccination	YES	NO
HBsAg (+) Total anti-HBc (+) IgM anti-HBc (+) Anti-HBs (-)	Acute Infection	NO	--
HBsAg (+) Total anti-HBc (+) IgM anti-HBc (-) Anti-HBs (-)	Chronic Infection	YES	YES, need to be on a NI for at for at least 12 week prior to start of Pembro without evidence of a flare

			during that period (ie, has been on chronic NI therapy) EXCLUDE IF: (a) <12 weeks of therapy; (b) HBV DNA not under control during this time frame; (c) Documented HBV flare in the past 12 weeks
HBsAg (-) Total anti-HBc (+) IgM anti-HBc (-) Anti-HBs (-) HBV DNA (negative)	Unclear. Could be: (1) Resolved infection (most common) (2) False positive anti-HBc (so actually NOT HBV infected) (3) Low Level infection (4) Resolving Acute infection	YES	NO

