12.1 Pre-Treatment Evaluations (Screening)

The following must be collected/ performed within 28 days prior to Cycle 1, day 1 of treatment. Clinical and laboratory evaluations performed as part of routine standard of care do not need to be repeated if performed within the appropriate window.

- Complete medical history, disease history and prior medical treatments
- Demographic data (age, gender, and race)
- Height
- Weight
- Vital signs (V/S)
 - Oral temperature
 - Blood pressure
 - Heart rate
- Complete physical examination (PE)
- ECOG Performance Status (PS)
- 12-Lead Electrocardiogram (ECG)
- Urine or serum pregnancy test for women of child-bearing potential (WoCBP)
- Complete Blood Count (CBC) with differential (diff)
- Coagulation studies:
 - PT/INR,
 - aPTT
- Comprehensive Serum Chemistry Panel (see Section 10.2.1 for hepatic toxicity guidelines)
 - Albumin,
 - Alkaline phosphatase (alk phos),
 - Total bilirubin,
 - Calcium (Ca),
 - Chloride (Cl),
 - Creatinine,
 - Potassium (K),
 - Total Protein,
 - SGOT (AST),
 - SGPT (ALT),
 - Sodium (Na),
 - Blood urea nitrogen (BUN),
 - Liver function tests (LFTs),
- Thyroid Tests
 - T3
 - T4
 - TSH
- Alpha-fetoprotein (AFP)
- Lipase,
- Amylase and,
- Hepatitis B Virus (HBV) Testing (see Section 10.2.1 for hepatic toxicity guidelines)

- HBsAg,
- HBsAb,
- anti-HBc antibody,
- HBeAg
- Hepatitis C Virus (HCV) Testing (see Section 10.2.1 for hepatic toxicity guidelines)
 - anti-HCV
- Urinalysis (U/A)
- Correlative Studies (See Section 1.5 and 13.0)
- Imaging Studies: Imaging studies for tumor assessment for all known sites of disease, (including triple phase CT or MRI of abdomen with contrast)
- Baseline symptoms

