12.6 Calendar of Clinical and Laboratory Evaluations

	Screening	Treatment Cycle(s) q21 days	Off Treatment ±5 days	Safety Evaluation	Follow-Up
	≤28 days prior ^A	Day 1 (±3 days unless specified)		30-days (+5 days) after Off Treatment	every 12 weeks ^K
ICF	X				
Eligibility	X				
Demographics ^B	X				
Complete Medical History ^C	X	X	X		
Height	X				
Weight	X	X	X	X	
Vital Signs ^D	X	X	X	X	
Complete PE	X	X	X	X	
ECOG PS	X	X	X	X	
12-Lead ECG	X				
CBC with diff	X	X	X	X	
Comp Serum Chemistry Panel ^E	X	X	X	X	
Alpha-fetoprotein (AFP)	X	X	X	X	
Lipase & Amylase	X	(X, repeat only if clinically indicated)			
T3, T4 and TSH	X	X	X	X	
PT/INR, aPTT	X			X	
HBV and HCV Testing	X (Section 12.1)	X (Section 10.2.1)			
Urine or serum pregnancy test ^F	X				
Urinalysis	X				
Correlative Studies: Tissue Sample ^G (Archival or newly obtained)	X				
Correlative Studies: Peripheral Blood ^H (Serum)	X	X ^H	X ^H	X ^H	
Imaging studies ^I	X	(X)	X		
Pembrolizumab IV administration		X			
Baseline Symptoms	X				
Adverse Events			X		(X) ^J
Concomitant Medications			X		
Telephone Call ^L					X

^A Screening evaluations should be done within 28-days prior unless otherwise specified.

^B Demographic data includes age, gender and racial/ethnic background.

^C Complete Medical History includes disease history and prior medical treatments.

^D Vital signs include oral temperature, blood pressure and heart rate.

^E Comprehensive Serum Chemistry Panel includes albumin, alkaline phosphatase, total bilirubin, sodium, calcium, chloride, creatinine, potassium, total protein, AST (SGOT), ALT (SGPT), blood urea nitrogen,.

- ^F Urine or serum (beta-HCG) pregnancy test is required for women of childbearing potential **within 3-days prior to Day 1** of trial treatment.
- ^G Tissue sample (either archival or newly obtained) is optional and for correlative studies (see Section 1.5 and 13.0 for details).
- ^H Serum collection for correlative studies is optional (see Section 1.5 and 13.0 for details). Samples will be collected at baseline, during treatment and/or at the time of documented disease progression, whichever occurs first.

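### Table 1 in Section 10.2.1 bars chronic HBV patients with a flare or uncontrolled HBV DNA in the past 12 weeks, but exclusion 20 has no such term and does not cite the table

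*Combined protocol and SAP*

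**What the plan says.** Exclusion 20 appears in the synopsis and in Section 5.2. Both open with "HCC patients with evidence of prior HBV must fulfill the following criteria in order to be eligible for the study". The entry conditions that follow in 5.2 are "HBV VL <100 IU/mL before study enrollment, and subjects with active HBV need to be on anti-HBV suppression ≥ 3 months", with suppression to continue during treatment and for 6 months afterwards. Neither version mentions a flare, a period of sustained DNA control, or Table 1.

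Two other places restate the entry rule without adding to it. Section 9.1.4 (immune-mediated hepatitis) says "a viral load <100 IU/mL is required for study entry, and with active HBV must have also been treated with antiviral therapy". The prose of 10.2.1 gives the same viral-load limit and adds "Those with active HBV must have been treated with antiviral therapy for ≥3 months before initiation of study treatment".

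Table 1 follows that prose and is titled as treatment guidance. Its chronic-infection row (HBsAg-positive, IgM anti-HBc-negative) requires at least 12 weeks on an NI before pembrolizumab without a flare. It then lists exclusions: less than 12 weeks of therapy, and "HBV DNA not under control during this time frame; (c) Documented HBV flare in the past 12 weeks". The acute-infection row is answered NO. The column holding these answers is labelled for KN-0224.

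On enrolment, Section 6.0 requires a "Completed and signed protocol-specific eligibility checklist" and a review of all eligibility requirements. In the Section 12.6 calendar, the screening entry for hepatitis testing is "X (Section 12.1)". Section 12.1 in turn lists "Hepatitis B Virus (HBV) Testing (see Section 10.2.1 for hepatic toxicity guidelines)".

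**The concern.** An entry criterion should give one answer for one patient. Here the criterion in the formal eligibility list is shorter than the one in a toxicity-section table, and the list gives no sign that the table exists. A site that takes eligibility from 5.2 would not ask about a recent flare. A site that also applies Table 1 would turn the same patient away.

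What is at stake is a pre-dose safeguard. The on-study protections (viral load every 3 weeks, interruption on reactivation) act only after the first dose. Section 9.1.3 gives a mean elimination half-life of 26 days, so interruption does not end exposure quickly. It also reports that two of four chimpanzees with chronic hepatitis B had raised liver enzymes on pembrolizumab, lasting at least a month after it was stopped. Those data do not concern recent flares specifically, but they suggest why the authors might want the virus quiet before dosing.

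**Working it through.** The plan states no figure on this point, so the check compares the rules and runs one patient through them.

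**Rules side by side**

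| Condition before first dose | Exclusion 20 (5.2, synopsis) | 9.1.4 | 10.2.1 prose | 10.2.1 Table 1, chronic row |
|---|---|---|---|---|
| Viral load <100 IU/mL | yes | yes | yes | not stated as a number |
| Time on antiviral therapy | ≥3 months if active | ≥3 months if active | ≥3 months if active | ≥12 weeks |
| HBV DNA controlled over the 12 weeks | no | no | no | yes |
| No documented flare in the past 12 weeks | no | no | no | yes |

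The shorter rule stands in 4 places (synopsis, 5.2, 9.1.4, 10.2.1 prose) and the fuller rule in 1 (Table 1).

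**Test patient (assumed for illustration).** HBsAg-positive, chronic infection, 120 days on an NI, documented flare 56 days ago, viral load now below 100 IU/mL. The flare came 120 − 56 = 64 days into therapy.

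1. *Duration.* 12 weeks = 12 × 7 = 84 days; 3 calendar months is at most 92 days. Since 120 > 92 > 84, both duration rules are met.
2. *Viral load at entry.* Below 100 IU/mL, so this condition of exclusion 20 is met.
3. *Exclusion 16* (uncontrolled illness, including active infection). The flare is now suppressed, so this does not clearly apply.
4. *Result under 5.2.* Eligible on HBV grounds.
5. *Table 1, flare item.* 56 < 84, so the patient is excluded. If HBV DNA rose with the flare, the DNA-control item excludes as well.

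The two texts give opposite answers, and the difference comes from what happened during the preceding 84 days, not from the patient's state at entry.

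**Acute infection.** Table 1 answers NO and exclusion 20 does not name it. Most acute cases would nevertheless fail the viral-load limit, the 3-month rule for active HBV, exclusion 16, or the transaminase and bilirubin limits in inclusion 11. No wrongly admitted acute case has been shown.

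**The case against.** The strongest reply is that the rules are cumulative. Exclusion 20 does not say that every patient who meets it must be admitted. The prose of 10.2.1 itself speaks of study entry, and Table 1 follows it. The calendar's screening cell leads to 12.1, and 12.1 leads to 10.2.1. Section 6.0 requires all eligibility requirements to be reviewed. A careful site would therefore reach the table and exclude the patient.

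Much of this stands: a route to the table exists, and a cumulative reading resolves the case in favour of exclusion. But 12.1 cites 10.2.1 as toxicity guidance, the table is titled as treatment guidance, and its inclusion column carries a study label that the protocol does not explain. A reader who arrives there cannot be sure that the column governs entry to this trial.

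Several stronger readings are tempting, and the documents do not support them:

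- *That patients with a recent flare will be dosed because the checklist omits the question.* The checklist is not in the documents, so its content is conjecture.
- *That patients with uncontrolled HBV DNA at entry, or with acute infection, get through.* The viral-load limit tests DNA at entry, and acute infection is largely caught elsewhere.
- *That 12 weeks and 3 months conflict.* Exclusion 20 is slightly the stricter, by up to 92 − 84 = 8 days, and a patient who meets it meets both.
- *That the result of the trial is affected because Section 16.3 limits the main analysis set to eligible patients.* The test patient's eligibility status is indeed unclear, but nothing in the documents allows an effect on the disease control rate or on the Simon boundaries to be shown.

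**Conclusion.** The point holds in a narrow form. For chronic HBsAg-positive patients, Table 1 imposes a 12-week condition (no documented flare, HBV DNA under control) that exclusion 20 lacks and does not cite. An identifiable patient is eligible under one text and excluded under the other.

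This is a minor safety clarification. It concerns a subgroup whose size cannot be computed, since the documents give no HBV prevalence. Patients at or above 100 IU/mL are already barred, and on-study viral monitoring applies to those admitted.

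The conclusion assumes that Table 1 is meant to govern this trial. If it was carried over from another study and is not meant to bind, the patient is eligible and the table misleads; the text needs correcting either way.

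**What to change.** Keep exclusion 20 as it stands: viral load below 100 IU/mL, suppression for at least 3 months beforehand where HBV is active, throughout treatment and for 6 months after. Do not replace 3 months with 12 weeks, which would loosen the criterion by up to 8 days.

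Add to exclusion 20, in both 5.2 and the synopsis: no documented HBV flare, and HBV DNA under control, during the 12 weeks before first dose; acute HBV infection excluded (see Table 1, Section 10.2.1). Relabel the table's inclusion column for this study. If the sponsor does not intend the table to bind, it should say so there instead, though that would give up the pre-dose safeguard.

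The cost is amendment wording and slightly narrower HBV entry.

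Optional clarifications in the same amendment:

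- Define active HBV, a term on which the HBsAg-negative, DNA-positive row depends, and align the wording of 8.4.1 with it.
- Say what counts as HBV DNA under control.
- List in 12.1 the baseline viral load that 10.2.1 already requires.
- Name IgM anti-HBc as a reflex test in HBsAg-positive patients, because Table 1 uses it to separate acute from chronic infection and the baseline lists say only anti-HBc antibody. This adds one assay on blood already drawn.

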11.0 TREATMENT DISCONTINUATION

Treatment may be discontinued for any of the following reasons:

- The patient demonstrates progression of disease by RECIST v1.1 (Exception: Patients may remain on the study if in the opinion of the Investigator, he/she is deriving clinical benefit from study treatment)
- The patient withdraws consent from the study
- The patient has not received study treatment for 21 days due to a medical/surgical events or logistical reasons not related to study therapy (e.g. elective surgery, unrelated medical events, patient vacation, and/or holidays).

- The patient experiences an adverse event that in the opinion of the Investigator makes continued study treatment an unacceptable risk
- Intercurrent illness prevents further treatment administration
- The patient has completed 24 months of uninterrupted treatment with pembrolizumab or 35 administrations of study medication, whichever is later. Note: 24 months of study medication is calculated from the date of first dose.
- The patient has confirmed Complete Response (CR) following 24 weeks of pembrolizumab; see Section 8.5.1 for full details
- The patient becomes pregnant (also see Section 15.6 and Appendix A for Expedited Adverse Event Reporting Requirements)
- The patient requires continuous treatment with a prohibited concomitant drug(s) for which no safe alternatives can be substituted
- The patient is significantly noncompliant with the requirements of the protocol

Should discontinuation of study therapy occur, all efforts should be made to execute/ report End-of-Treatment and Follow-up Evaluations as completely as possible and to determine/ document the reason for discontinuation (unless the patient withdraws consent for follow-up).

If a patient wishes to withdraw consent from the study, the PI must be notified. The information regarding withdrawal (i.e. subject identifiers and date of withdrawal) should be documented in the subject's record and updated within any other research database(s).

12.0 SCHEDULE OF CLINICAL & LABORATORY EVALUATIONS

Prior to performing any study-specific procedures or evaluations, written informed consent and authorization for the use of protected health information (HIPAA) must be obtained in accordance with all applicable policies, regulations and laws.

Correlative evaluations (optional) will also be performed at specified visits. Please refer to Section 1.5 and 13.0 CORRELATIVE STUDIES for details.

Imaging studies should be done *every 3 cycles (every 9 weeks, ±9 days)* from the date of Enrollment timed to coincide with the end of the prior treatment cycle; assessing all known sites of disease using the same type(s) of scan(s) that was/were performed at baseline.

All evaluations should be completed as detailed below, prior to the administration of trial treatment on Day 1 of each cycle. All evaluations will be administered on an outpatient basis.

